7.8 Efficacy and Safety

7.8.1 Subject Characteristics

- Demographic Data
- Medical History
- Wound and surrounding skin characteristics
- Secondary dressing and fixation characteristics

7.8.2 Efficacy Measurements and Variables

7.8.2.1 Main Objective

Variable

The main criterion corresponds to the percentage of non-painful dressing removals defined as the percentage of dressing removals associated with a value < 30 mm on a VAS assessing pain scale (0 to 100 millimeters) evaluated at the first dressing removal (V2, D3±2).

This 30 mm threshold is recognized to differentiate a weak pain (score <30 mm) from a moderate (score ≥30 mm) to severe (score >50 mm) one [9-12].

Measurement

Subjects will be asked by investigators to rate their pain intensity perceived at the first dressing removal (V2, D3±2). Pain assessment will be performed using a Visual Analog Scale (VAS). The VAS is a 100 mm straight line ranging from 0 to 100, on which the subject will indicate his/her pain. Subjects will beforehand be informed that the beginning of the scale refers to "no pain" (0) and the end to the most severe intensity of pain they can have (100). Painless dressing change is defined as pain < 30 mm on the VAS. The results obtained during the first dressing removal visit (V2, D3±2) will be filled in by the investigator in the CRF.

7.8.2.2 Secondary Objectives

Variables

Secondary efficacy criteria will be as follows:

- Complete healing at V3 (D21+2 or earlier, as soon as the wound is epithelialized completely).
- Wound condition assessment at V2 and V3 or ET
- Surrounding skin condition assessment at V2 and V3 or ET
- Global assessment of the dressing by the investigator at V2 and V3 or ET
- Global assessment of exudate management (efficiency of the CL to drain exudates to the secondary dressing)
- Global assessment of the dressing by the subject at V3 or ET
- Assessments from study nurse's booklet (at each dressing change)
- Adverse events (AEs), serious adverse events (SAEs), device effects (ADEs), serious device effects (SDEs), device deficiencies (DDs), occurring during the investigation

Measurements

Complete healing at V3

The evaluation of complete healing status (100% of epithelialization (first epithelia layer) of the wound) will be performed by the investigator at V3 (D21 \pm 2 or earlier if the wound is

healed before D21), as the phenomenon of epithelialization is visible to the naked eye). Data on complete healing will be reported in the CRF.

In addition to the evaluation of complete healing status performed by the investigator at V3, a blind assessment of healing will be performed by an independent assessor - chosen prior to the start of investigation - on photographs taken by investigators at V1 and at the final visit (V3). All photographs will be taken of the wound site and adjacent intact skin under standardized conditions (see Appendix 17.2). The digital photographs will be captured and available to the independent assessor chosen. A blind assessment of these photographs will be performed using W.H.A.T. in order to evaluate the healing status.

Wound condition assessment

Bleeding of the wound bed

The investigator will have to report the possible occurrence and intensity of bleeding at each dressing removal (including V1).

Maceration of the wound

Maceration refers to the skin changes seen when moisture is trapped against the skin for a prolonged period. The investigator will evaluate this parameter at each dressing removal (including V1).

Inflammation

The investigator will evaluate the presence of inflammation at the V1 and at each dressing removal.

• Infection

The investigator will evaluate the presence of infection at the V1 and at each dressing removal. (According to the investigation plan, presence of the infection is an exclusion criterion and the reason for the discontinuation of the patients from the study).

Necrotic/Fibrinous/Granulation/Epithelisation Tissue ratio

The investigator will assess wound necrotic/ fibrinous/ granulation/ epithelisation tissue ratio at the V1 and at each dressing removal.

In-growth in the dressing holes

The investigator will collect information on the wound tissue in-growth in the dressing holes at the V1 and at each dressing removal.

Surrounding skin condition assessment

Each of the following parameters will be evaluated at V1, V2 (D3±2) and V3 (D21+2 or earlier, as soon as the wound is epithelialized completely) or ET:

Inflammatory signs

(Inflammation is characterized by 4 main signs: erythema, oedema, warmth and pain)

Infection

(Deposition and multiplication of bacteria in tissue with an associated host reaction. The classic local signs of infection include: localised erythema, localised pain, localised heat, cellulitis and oedema; there may also be present specific exudation, smell, delayed healing, abscess, general symptoms. Presence of the infection is an exclusion criterion and the reason for the discontinuation of the patients from the study)

Irritation

(Irritation is synonymous of irritant contact dermatitis which is a secondary inflammation of the skin due to an irritant or caustic agent)

Allergic rash/eczema
 (Cutaneous hypersensitivity reaction induced by a skin contact with an allergenic substance)

Blistering

(Uprising of a part of the epidermis, drawing a projection and thus achieving a bubble that contains a variable fluid)

Skin stripping

(Skin stripping is caused by the repeated application and removal of adhesive tapes and dressings from the skin. This process inflicts variable levels of damage to the layers of the stratum corneum, and may cause inflammatory skin damage, oedematous changes, skin soreness and a detrimental effect on skin barrier function)

Maceration

(Maceration refers to the skin changes seen when moisture is trapped against the skin for a prolonged period. The skin will turn white or grey and will soften and wrinkle)

- Dry
- Trauma to wound edges (Trauma corresponds to underlying lesions or to retraction of wound edges)
- Product degradation on the skin
- Hematoma
- Other

Global assessment of the dressing by the investigator

The dressing use will be evaluated by means of a specific questionnaire to be completed by the investigator at V2 and V3 or ET: ease of handling, ability to maintain its integrity, ease of application, ability to be repositioned, conformability, wound adhesion, ability of dressings to stay in place, transparency, ability to transfer wound fluid to the secondary dressing, ease/speed of removal, absence of residue, overall impression.

Global assessment of the dressing by the subject

The dressing use will be evaluated by means of a specific questionnaire to be completed by the subject at the end of the study (V3 or ET): ease of handling, ability to maintain its integrity, ease of application, ability to be repositioned, ability of dressings to stay in place, transparency, comfort of the patient, ability to transfer wound fluid to the secondary dressing,

ease/speed of removal, overall impression.

Assessments from the study nurse's booklet

For any additional dressing changes what will occur between V2 and V3, the study nurse will be asked to report at each dressing change in his/her booklet carefully and legibly: number of the additional visit, date of the visit, reason for dressing change, presence of complete reepithelialization, appearance of the dressing before removal, bleeding during dressing removal, appearance of the wound bed, appearance of the surrounding skin, amount of exudate, wound moisture, local treatment, number of dressings used, application of dressing, secondary dressing, initials of person in charge of dressing change.

7.8.3 Safety Measurements and Variables

Safety measurements include AEs, ADEs, Serious Adverse Events (SAEs)/Serious Adverse Device Effects (SADEs), and Device Deficiencies (DDs) evaluations. The definition of AE, ADE, SAE, SADE, and DD and procedures for reporting SAEs, SADEs and DDs that could have led to a SADE are presented in section 8 of this Clinical Investigational Plan (CIP). All AEs, ADEs, SAEs, SADEs and DDs must be recorded in the appropriate form of the CRF. It is of utmost importance that all staff involved in the investigation is familiar with the content of section 8. It is the responsibility of the principal investigator to ensure this.

7.8.4 Anticipated ADEs

Anticipated local adverse events (e.g. events occurring at wound site) may be categorized as:

- Wound worsening secondary to wound infection or repeated traumatic injury.
- Device related such as contact dermatitis or dressing-induced skin irritation or wound bed injury at dressing removal.

Some examples of events which are not anticipated ADEs: bleeding, pain, adhesion to the dressing.

Pre-existing diseases (before application of the medical device) are not documented as adverse events but as medical history. New diseases and pre-existing diseases that worsen during the trial are documented as AEs.

7.9 Statistical methods and determination of sample size

7.9.1 Statistical Evaluation

The statistical analyses will be performed using the software SAS (version 9.4 or higher).

7.9.1.1 Population Analyses

Analyses will be performed on three populations as follows:

• The Safety population consists of all subjects allocated to treatment sample; and who had at least one investigational product applied.

- All randomized subjects with at least one exposure to either dressing will be included in the modified intent-to-treat (mITT) population. Subjects will be analysed in the treatment groups to which they will be randomly assigned (as per ITT principle).
- The per-protocol (PP) population consists of all enrolled subjects who satisfied the entry criteria of the investigation, who had an assessment of main criterion at V2 and who completed the treatment without major violations of the protocol.

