	 Patients unable to manifest an oral consent to participate (e.g. dementia) or to understand the use of the VAS tool Patient not covered by health insurance/social security 						
Study Duration	24 months						
Number of patients	168 patients (i.e. 84 per group)						
•	' ' ' ' ' ' ' ' ' ' ' ' ' ' ' ' ' ' '						
Treatment duration and visits schedule	3 weeks: V1 (D0), V2 (D3±2) and V3 (D21+2 or earlier, as soon as the wound is epithelialized completely)						
Treatment duration	3 weeks: V1 (D0), V2 (D3±2) and V3 (D21+2 or earlier, as soon as						
Treatment duration	3 weeks: V1 (D0), V2 (D3±2) and V3 (D21+2 or earlier, as soon as the wound is epithelialized completely)						
Treatment duration	3 weeks: V1 (D0), V2 (D3±2) and V3 (D21+2 or earlier, as soon as the wound is epithelialized completely) Primary endpoint: Percentage of wound dressing changes associated with a pain <30						
Treatment duration	3 weeks: V1 (D0), V2 (D3±2) and V3 (D21+2 or earlier, as soon as the wound is epithelialized completely) Primary endpoint: Percentage of wound dressing changes associated with a pain <30 mm on VAS at V2 (D3±2).						
Treatment duration	3 weeks: V1 (D0), V2 (D3±2) and V3 (D21+2 or earlier, as soon as the wound is epithelialized completely) Primary endpoint: Percentage of wound dressing changes associated with a pain <30 mm on VAS at V2 (D3±2). Secondary endpoint • Complete healing at V3 (Day D21+2 or earlier, as soon as the wound is epithelialized completely): Percentage of						
Treatment duration	3 weeks: V1 (D0), V2 (D3±2) and V3 (D21+2 or earlier, as soon as the wound is epithelialized completely) Primary endpoint: Percentage of wound dressing changes associated with a pain <30 mm on VAS at V2 (D3±2). Secondary endpoint • Complete healing at V3 (Day D21+2 or earlier, as soon as the wound is epithelialized completely): Percentage of epithelialization of the wound at V3 calculated based on a						
Treatment duration and visits schedule	3 weeks: V1 (D0), V2 (D3±2) and V3 (D21+2 or earlier, as soon as the wound is epithelialized completely) Primary endpoint: Percentage of wound dressing changes associated with a pain <30 mm on VAS at V2 (D3±2). Secondary endpoint • Complete healing at V3 (Day D21+2 or earlier, as soon as the wound is epithelialized completely): Percentage of						

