7.3.3 Early Termination/ Withdrawal of subjects from treatment or assessment

Patients are free to withdraw from participation in the study at any time upon request and without any disadvantages for their further care.

An investigator may discontinue a patient from the study for the following reasons:

- The identification of unacceptable risks, or incidents leading to an unacceptable benefit-risk assessment
- Premature termination of the investigation decided by the Sponsor
- Lost to follow-up
- Occurrence or development of a condition described in the exclusion criteria (i.e. pregnancy, infection of the wound) throughout the investigation
- Death

The reason for patient discontinuation or withdrawal from the study will be recorded on the Case Report Form (CRF) in the early termination visit.

Subjects who discontinue the investigation should always be asked about the presence of any Adverse Events/Adverse Device Effects or Device Deficiencies and, if possible, be assessed by the investigator as per the list of the Early termination visit procedures. Serious Adverse Events/Adverse Device Effects should be followed up until the resolution of the event.

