7.9.1.2 Efficacy analyses

Analysis of the main criterion

The test for the non-inferiority of Lomatuell Pro® vs UrgoTul® for the main criterion will be carried out through a confidence interval (CI) approach. Non-inferiority will be established if the lower unilateral limit of the 97.5% CI in the PP population for the between-treatment difference (Lomatuell Pro® - UrgoTul®) in the percentage of wound dressing associated with a pain < 30 mm on VAS at V2 does not exceed -10%.

Considering that the studied population is "patients with an acute wound" and that the primary endpoint will be assessed at V2 (Day 3±2); we can expect very few drop-outs. We also expect few patients with a major protocol deviation. Therefore, we can conclude that an assumption of 10% attrition rate is acceptable for this study.

In order to unambiguously conclude to non-inferiority in agreement with most of guidelines, the same analysis will be performed on the mITT population. In case of missing data to evaluate the primary criterion, the subjects will be considered as failures. The trial will be considered positive if both approaches support noninferiority.

Adjustment

The frequency of analgesic intake will also be analysed. In case of a significant difference between the 2 dressing groups, the analysis of the primary criterion (painless dressing removals) will be adjusted using a Mantel-Haenszel test.

Analysis of the secondary criteria

The following statistical tests will be used to analyse the secondary criteria according to the criteria type:

- Qualitative nominal criteria will be compared using a Chi² test.
- Qualitative ordinal criteria will be compared using a Mann-Whitney-Wilcoxon test
- Quantitative criteria will be compared using an analysis of variance (ANOVA)

Degree of significance

The criteria for which the degree of significance of the bilateral test will not exceed 0.05 (statistically significant difference) will highlight the specificities between the 2 groups of dressing.

Percentage of complete healing at V3

A wound will be considered as completely healed when there is 100% of epithelialization (first epithelia layer) of the wound. The percentage of wounds healed will be calculated based on a blind assessment from photographs using W.H.A.T.

Assessment of the wound condition

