10.2 Protocol Deviations

General definition: major protocol deviations are any protocol deviations that might significantly affect the completeness, accuracy, or reliability of the study data or that might significantly affect a subject's rights, safety, or well-being. Relevant major protocol deviations may include errors in treatment assignment, the use of excluded medication, poor compliance, loss to follow-up and missing data (cf. ICH E3. Questions and answers (R1). January 2013 and ICH E9).

In this trial, the following protocol deviations will be considered as major and will therefore lead to exclude patients from the PP set:

- Patient randomized while an inclusion criterion is not met
- Patient randomized while an exclusion criterion is met
- Patient not treated as per protocol between V1 (D0) and V2 (D3±2):
 - Patient randomized to Lomatuell Pro® but actually received UrgoTul® at D0
 - o Patient randomized to UrgoTul® but actually received Lomatuell Pro® at D0
- Pain assessment (VAS) during removal at V2 (D3±2) is missing (i.e. primary endpoint is missing)
- Pain assessment (VAS) during removal at V2 performed out of the time-window (i.e. at D6 or later)

Further major protocol deviations may be defined during the conduct of the trial, if deemed relevant. The list of major protocol deviations will have to be finalized and documented (for example, in the data review minutes) prior to the database lock.

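### Section 7.9.1.1, read literally, limits the per-protocol set to treatment completers, although the primary endpoint is taken at V2 and the exclusion list in section 10.2 stops there

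*Protocol*

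**What the plan says.** **PP definition.** Protocol 7.9.1.1 sets three conditions: the patient met the entry criteria, had the main criterion assessed at V2, and was one "who completed the treatment without major violations of the protocol". It does not define completion. The synopsis gives the treatment duration as "3 weeks: V1 (D0), V2 (D3±2) and V3 (D21+2 or earlier, as soon as" the wound has fully epithelialized.

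**Endpoint.** Section 7.8.2.1 has the primary variable "evaluated at the first dressing removal (V2, D3±2"), and only there.

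**Decision rule.** Section 7.9.1.2 states: "Non-inferiority will be established if the lower unilateral limit of the 97.5% CI in the PP population" lies within the 10-point margin. It repeats the analysis in mITT, with missing primary values counted as failures, and adds: "The trial will be considered positive if both approaches support noninferiority". mITT has no completion condition: "All randomized subjects with at least one exposure to either dressing will be included in the modified intent-to-treat (mITT) population".

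**Exclusion list.** Section 10.2 names the deviations that remove a patient from PP: entry-criterion breaches, the wrong dressing at D0, and a V2 VAS that is missing or too late. Its treatment item reads "Patient not treated as per protocol between V1 (D0) and V2 (D3±2"). Stopping after V2 is not listed, but deviations may be added until database lock.

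**Later exits.** Section 7.3.3 allows discontinuation for "Occurrence or development of a condition described in the exclusion criteria (i.e. pregnancy, infection of the wound) throughout the investigation". Section 13 foresees a change of treatment if the dressing is not tolerated.

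**SAP.** Section 4 of the supplied SAP says it is based on the protocol of a different product (Suprasorb C). It gives no PP rule for this trial that could settle the point.

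**The concern.** The V2 assessment is already a separate condition in 7.9.1.1, so the completion clause most naturally adds a requirement that applies after V2. Two statisticians could then build different primary sets from the same protocol, one from 7.9.1.1 and one from 10.2.

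Under the literal rule, membership depends on events after the outcome has been recorded. Infection, intolerance and withdrawal may be related to the dressing and to the pain already reported. Dropping such patients discards valid primary data and can shift the PP difference in either direction. It also undercuts the attrition allowance, which 7.9.1.2 justifies by the early endpoint and which therefore takes no account of losses between V2 and V3.

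**Working it through.** **Inputs from protocol 7.9.2.** Success rate 95% in both arms, margin 10 points, one-sided alpha 2.5%, power 80%, 75 evaluable per group, 10% attrition, 84 randomized per group.

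**Step 1: reproduce the plan.**
- n = (1.960 + 0.842)² × 2 × 0.95 × 0.05 / 0.10² = 74.6, so 75 per group.
- 75 / 0.90 = 83.3, so 84 per group.
- At 75 per group, SE = √(2 × 0.0475 / 75) = 0.0356. Power = Φ(0.10 / 0.0356 − 1.960) = Φ(0.850) = 80.2%.

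The stated figures reproduce.

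**Step 2: power if completion is required.** The documents give no post-V2 loss rate, so the rates here are assumptions. With the full 10% lost by V2, 84 × 0.90 = 75.6 remain per group.

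| Further loss after V2 | PP per group | Power | Randomized per group for 75 evaluable |
|---|---|---|---|
| 0% | 75 | 80.2% | 84 |
| 5% | 75.6 × 0.95 → 71 | 78.0% | 75 / (0.90 × 0.95) → 88 |
| 10% | 75.6 × 0.90 → 68 | 76.3% | 75 / (0.90 × 0.90) → 93 |
| 20% | 75.6 × 0.80 → 60 | 71.0% | 75 / (0.90 × 0.80) → 105 |

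If 10% covers all losses through V3, 75.6 per group remain and power is about 80%. A total loss of 15% leaves 84 × 0.85 = 71.4 and 78.3%.

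**Step 3: selective exits that favour the test dressing.** Take true rates of 85% v 95% (at the margin), 75 per arm, no missing V2 scores and the unpooled normal confidence limit, with exact binomial enumeration. Let 0%, 25% or 50% of Lomatuell Pro patients with a painful removal leave PP later (assumed).
- Expected Lomatuell Pro rate in PP: 85%; 0.85 / (0.85 + 0.15 × 0.75) = 88.3%; 0.85 / (0.85 + 0.15 × 0.50) = 91.9%.
- PP alone passes: 3.7%, about 14%, about 42%.
- PP and mITT together pass: 3.7% in all three cases.

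The joint rate does not move because mITT keeps every V2 score, and dropping test-arm failures only makes PP easier to pass. The excess of 3.7% over the nominal 2.5% comes from the normal approximation at these proportions and sample size; it is present with no removal at all.

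The exits need not differ by arm. If 5% of painless and 40% of painful removals stop later in both arms (assumed), the PP rates become 0.85 × 0.95 / (0.85 × 0.95 + 0.15 × 0.60) = 90.0% and 0.95 × 0.95 / (0.95 × 0.95 + 0.05 × 0.60) = 96.8%. The difference is −6.8 points instead of −10.

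**Step 4: selective exits that harm the test dressing.** Take both arms truly at 95%, with 0%, 25% or 50% of UrgoTul patients with a painful removal leaving PP later (assumed).
- Expected UrgoTul rate in PP: 95%; 0.95 / (0.95 + 0.05 × 0.75) = 96.2%; 0.95 / (0.95 + 0.05 × 0.50) = 97.4%.
- PP and mITT together pass: about 82%, 76%, 70%.

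Here PP is the harder test, and passing mITT cannot compensate.

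**The case against.** The strongest reply is that section 10.2 is the operative rule. On that view the clause in 7.9.1.1 is one condition, treatment without major violations, and 10.2 says what those violations are; none concerns stopping after V2. This reading is possible, and it means the protocol cannot be said to require completion without doubt. It does not close the matter, because 10.2 does not say that it replaces the completion wording and its list stays open until database lock.

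A reader might infer that anyone who does not reach D21 is dropped. The documents do not support this: treatment ends earlier when the wound epithelializes, so a patient who heals early has completed it.

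A reader might also take the PP-alone pass rates of about 14% and 42% as the trial's error rate. They are not. Both analyses must succeed, and the joint rate stays at about 3.7% in that scenario.

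Finally, every post-V2 loss rate used here is assumed, and the one-sided exit patterns are deliberately unfavourable. The protocol expects few drop-outs and few major deviations by V2, so part of the 10% allowance may be left to absorb later losses. That stands: the size of the effect in this trial is unknown and may be small.

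**Conclusion.** The point holds as an internal conflict with a possible effect on the primary result. Section 7.9.1.1 read literally makes PP membership depend on events after the endpoint; section 10.2 and the attrition argument in 7.9.1.2 imply that it should not.

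Under the literal rule, the power cost is about 2 to 9 points for an assumed further loss of 5% to 20% on top of a full 10%, and essentially nil if all losses through V3 stay within 10%. A rise in the trial's false-positive rate is not supported, since mITT must also pass. What remains is a PP analysis that adds no protection when exits favour the test dressing, and that can make a truly non-inferior dressing fail when exits fall on comparator patients with painful removals (joint success about 82% down to 76% or 70% under the assumed 25% or 50%). The correction should be made before database lock.

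**What to change.** In 7.9.1.1, define PP for the primary endpoint as patients who met the entry criteria, had a V2 VAS assessment, and had no major deviation under 10.2 up to and including that assessment. Delete the completion condition. A separate completer set may be kept for the V3 endpoints. In 10.2, state that any deviation added later for this set must concern events up to V2. The SAP that applies to this trial should carry the same definition.

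The cost is one revised sentence in 7.9.1.1 and one limiting phrase in 10.2. Data collection does not change, valid V2 scores are kept, and the sample size stays at 75 evaluable and 84 randomized per group.
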